Monocytes (ABS)	MONOABS	Giga/L	1.00000	10 ⁹ /L
Neutrophils (REL)	NEUT%	%	1.00000	%
Neutrophils (REL)	NEUT%	Proportion of 1.0	100.00000	%
Neutrophils (REL)	NEUT%	Fraction	100.00000	%
Neutrophils (ABS)	NEUTABS	/cumm	0.00100	10 ⁹ /L
Neutrophils (ABS)	NEUTABS	/mm ³	0.00100	10 ⁹ /L
Neutrophils (ABS)	NEUTABS	10 ⁶ /L	0.00100	10 ⁹ /L
Neutrophils (ABS)	NEUTABS	/µL	0.00100	10 ⁹ /L
Neutrophils (ABS)	NEUTABS	k/µL	1.00000	10 ⁹ /L
Neutrophils (ABS)	NEUTABS	10 ³ /µL	1.00000	10 ⁹ /L
Neutrophils (ABS)	NEUTABS	10 ³ /mm ³	1.00000	10 ⁹ /L
Neutrophils (ABS)	NEUTABS	10 ⁹ /L	1.00000	10 ⁹ /L
Neutrophils (ABS)	NEUTABS	/nL	1.00000	10 ⁹ /L
Neutrophils (ABS)	NEUTABS	Gpt/L	1.00000	10 ⁹ /L
Neutrophils (ABS)	NEUTABS	Giga/L	1.00000	10 ⁹ /L
Neutrophils Band Form (REL)	NEUTROPHILS BAND %	%	1.00000	%
Neutrophils Band Form (REL)	NEUTROPHILS BAND %	Proportion of 1.0	100.00000	%
Neutrophils Band Form (REL)	NEUTROPHILS BAND %	Fraction	100.00000	%
Neutrophils Band Form	NEUTROPHILS BAND ABS	/cumm	0.00100	10 ⁹ /L
Neutrophils Band Form	NEUTROPHILS BAND ABS	/mm ³	0.00100	10 ⁹ /L
Neutrophils Band Form	NEUTROPHILS BAND ABS	10 ⁶ /L	0.00100	10 ⁹ /L

Project Document Version No.:2.0; Document Effective Date: Date of last signature

TP-GDO-WW-016-09

Effective Date: 22 Dec 21

Related to: SOP-GDO-WW-019

Page 65 of 70

Parexel International

Rallybio IPA, LLC
IPA2202

Statistical Analysis Plan

LAB TEST DESCRIPTION (SDTM Labtest)	QUESTION	Collected Unit	Conversion Factor	PAREXEL Standard Unit for Presentation
Neutrophils Band Form	NEUTROPHILS BAND ABS	/ μ L	0.00100	10 ⁹ /L
Neutrophils Band Form	NEUTROPHILS BAND ABS	k/ μ L	1.00000	10 ⁹ /L
Neutrophils Band Form	NEUTROPHILS BAND ABS	10 ³ / μ L	1.00000	10 ⁹ /L
Neutrophils Band Form	NEUTROPHILS BAND ABS	10 ³ /mm ³	1.00000	10 ⁹ /L
Neutrophils Band Form	NEUTROPHILS BAND ABS	10 ⁹ /L	1.00000	10 ⁹ /L
Neutrophils Band Form	NEUTROPHILS BAND ABS	/nL	1.00000	10 ⁹ /L
Neutrophils Band Form	NEUTROPHILS BAND ABS	Gpt/L	1.00000	10 ⁹ /L
Neutrophils Band Form	NEUTROPHILS BAND ABS	Giga/L	1.00000	10 ⁹ /L
Platelet Count	PLT	/cumm	0.00100	10 ⁹ /L
Platelet Count	PLT	/mm ³	0.00100	10 ⁹ /L
Platelet Count	PLT	10 ⁶ /L	0.00100	10 ⁹ /L
Platelet Count	PLT	/ μ L	0.00100	10 ⁹ /L
Platelet Count	PLT	k/ μ L	1.00000	10 ⁹ /L
Platelet Count	PLT	10 ³ / μ L	1.00000	10 ⁹ /L
Platelet Count	PLT	10 ³ /mm ³	1.00000	10 ⁹ /L
Platelet Count	PLT	10 ⁹ /L	1.00000	10 ⁹ /L
Platelet Count	PLT	/nL	1.00000	10 ⁹ /L
Platelet Count	PLT	Gpt/L	1.00000	10 ⁹ /L
Platelet Count	PLT	10 ⁴ / μ L	10.00000	10 ⁹ /L
Platelet Count	PLT	10 ⁵ / μ L	100.00000	10 ⁹ /L
Platelet Count	PLT	Giga/L	1.00000	10 ⁹ /L
Potassium (K)	POTASSIUM	mEq/L	1.000	mmol/L
Potassium (K)	POTASSIUM	mmol/L	1.000	mmol/L

Project Document Version No.:2.0; Document Effective Date: Date of last signature

TP-GDO-WW-016-09

Effective Date: 22 Dec 21

Related to: SOP-GDO-WW-019

Page 66 of 70

Parexel International

Rallybio IPA, LLC
IPA2202

Statistical Analysis Plan

LAB TEST DESCRIPTION (SDTM Labtest)	QUESTION	Collected Unit	Conversion Factor	PAREXEL Standard Unit for Presentation
Total Protein	PROTEIN TOTAL	g/L	1	g/L
Total Protein	PROTEIN TOTAL	g/dL	10	g/L
Total Protein	PROTEIN TOTAL	g%	10	g/L
Prothrombin Time Ratio	Prothrombin Time Ratio	Ratio	1.00000	Ratio
Prothrombin Time Ratio	Prothrombin Time Ratio	%	0.01000	Ratio
Prothrombin Time	Prothrombin Time SEC	Sec	1.00000	Sec
Red Blood Cell	Red Blood Cell	/cumm	0.000001	10 ¹² /L
Red Blood Cell	Red Blood Cell	/mm ³	0.000001	10 ¹² /L
Red Blood Cell	Red Blood Cell	10 ⁶ /L	0.000001	10 ¹² /L
Red Blood Cell	Red Blood Cell	/µL	0.000001	10 ¹² /L
Red Blood Cell	Red Blood Cell	M/µL	1.00000	10 ¹² /L
Red Blood Cell	Red Blood Cell	10 ⁶ /µL	1.00000	10 ¹² /L
Red Blood Cell	Red Blood Cell	10 ⁶ /mm ³	1.00000	10 ¹² /L
Red Blood Cell	Red Blood Cell	/pL	1.00000	10 ¹² /L
Red Blood Cell	Red Blood Cell	Tpt/L	1.00000	10 ¹² /L
Red Blood Cell	Red Blood Cell	T/L	1.00000	10 ¹² /L
Red Blood Cell	Red Blood Cell	10 ¹² /L	1.00000	10 ¹² /L
Reticulocytes (REL)	RETIC%	%	1.00000	%
Reticulocytes (REL)	RETIC%	Proportion of 1.0	100.00000	%
Reticulocytes (REL)	RETIC%	Fraction	100.00000	%
Reticulocytes (REL)	RETIC%	Promille	0.1	%
Reticulocytes (REL)	RETIC%	%o	0.1	%
Reticulocytes (REL)	RETIC%	0/00	0.1	%

Project Document Version No.:2.0; Document Effective Date: Date of last signature

TP-GDO-WW-016-09

Effective Date: 22 Dec 21

Related to: SOP-GDO-WW-019

Page 67 of 70

Parexel International

Rallybio IPA, LLC
IPA2202

Statistical Analysis Plan

LAB TEST DESCRIPTION (SDTM Labtest)	QUESTION	Collected Unit	Conversion Factor	PAREXEL Standard Unit for Presentation
Reticulocytes (ABS)	RETICUAB	/cumm	0.00100	10 ⁹ /L
Reticulocytes (ABS)	RETICUAB	/mm ³	0.00100	10 ⁹ /L
Reticulocytes (ABS)	RETICUAB	10 ⁶ /L	0.00100	10 ⁹ /L
Reticulocytes (ABS)	RETICUAB	/µL	0.00100	10 ⁹ /L
Reticulocytes (ABS)	RETICUAB	k/µL	1.00000	10 ⁹ /L
Reticulocytes (ABS)	RETICUAB	10 ³ /µL	1.00000	10 ⁹ /L
Reticulocytes (ABS)	RETICUAB	10 ³ /mm ³	1.00000	10 ⁹ /L
Reticulocytes (ABS)	RETICUAB	10 ⁹ /L	1.00000	10 ⁹ /L
Reticulocytes (ABS)	RETICUAB	/nL	1.00000	10 ⁹ /L
Reticulocytes (ABS)	RETICUAB	Gpt/L	1.00000	10 ⁹ /L
Reticulocytes (ABS)	RETICUAB	/cumm	0.00100	10 ⁹ /L
Reticulocytes (ABS)	RETICUAB	/mm ³	0.00100	10 ⁹ /L
Reticulocytes (ABS)	RETICUAB	10 ⁶ /L	0.00100	10 ⁹ /L
Reticulocytes (ABS)	RETICUAB	/µL	0.00100	10 ⁹ /L
Reticulocytes (ABS)	RETICUAB	M/µL	1000.00000	10 ⁹ /L
Reticulocytes (ABS)	RETICUAB	10 ⁶ /µL	1000.00000	10 ⁹ /L
Reticulocytes (ABS)	RETICUAB	10 ⁶ /mm ³	1000.00000	10 ⁹ /L
Reticulocytes (ABS)	RETICUAB	/pL	1000.00000	10 ⁹ /L
Reticulocytes (ABS)	RETICUAB	Tpt/L	1000.00000	10 ⁹ /L
Reticulocytes (ABS)	RETICUAB	T/L	1000.00000	10 ⁹ /L
Reticulocytes (ABS)	RETICUAB	Giga/L	1.00000	10 ⁹ /L
Sodium (NA)	SODIUM	mEq/L	1.000	mmol/L
Sodium (NA)	SODIUM	mmol/L	1.000	mmol/L

Project Document Version No.:2.0; Document Effective Date: Date of last signature

TP-GDO-WW-016-09

Effective Date: 22 Dec 21

Related to: SOP-GDO-WW-019

Page 68 of 70

LAB TEST DESCRIPTION (SDTM Labtest)	QUESTION	Collected Unit	Conversion Factor	PAREXEL Standard Unit for Presentation
Urea	UREA	mg/dL	0.167	mmol/L
Urea	UREA	g/L	16.650	mmol/L
Urea	UREA	mmol/L	1.000	mmol/L
Urea	UREA	mg%	0.167	mmol/L
Urea	UREA	µmol/L	0.001	mmol/L
Urea	UREA	mg/L	0.0167	mmol/L
White Blood Cells	WBC	/cumm	0.00100	10 ⁹ /L
White Blood Cells	WBC	/mm ³	0.00100	10 ⁹ /L
White Blood Cells	WBC	10 ⁶ /L	0.00100	10 ⁹ /L
White Blood Cells	WBC	/µL	0.00100	10 ⁹ /L
White Blood Cells	WBC	k/µL	1.00000	10 ⁹ /L
White Blood Cells	WBC	10 ³ /µL	1.00000	10 ⁹ /L
White Blood Cells	WBC	10 ³ /mm ³	1.00000	10 ⁹ /L
White Blood Cells	WBC	10 ⁹ /L	1.00000	10 ⁹ /L
White Blood Cells	WBC	/nL	1.00000	10 ⁹ /L
White Blood Cells	WBC	10 ² /µL	0.10000	10 ⁹ /L
White Blood Cells	WBC	Gpt/L	1.00000	10 ⁹ /L
White Blood Cells	WBC	Giga/L	1.00000	10 ⁹ /L

7. References

1. *Development of standard definitions and grading for Maternal and Fetal Adverse Event Terminology.* Spencer R, Hecher K, Norman G, Marsal K, Deprest J, Flake A, et al. 1, s.l. : Prenatal Diagnosis, January 2022, Prenatal Diagnosis, Vol. 42. 1097-0223.

<https://doi.org/10.1080/17518423.2024.2374534>

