4.1.3.2. Relative Day

Wherever data are summarized over time, study day will be calculated in relation to date of first treatment. If no value exists before the first dose/administration, then the baseline value will be treated as missing. Unless time variables indicate otherwise, AEs occurring on the day of first dose will be assumed to have occurred after first dose and will be assumed to be TE. The relative day for an assessment will be calculated from the first dosing date of the study drug and derived as follows:

- For days prior to the first dose = Assessment Date – first dosing date.
- For post-dose relative days = Assessment Date – first dosing date +1.

The relative day will be included in relevant listings.

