4.1.3.3. Analysis Visit Window

The protocol specified visit windowing will be followed for all assessments (see [Table 3](#) and [Table 4](#)). If multiple visits occur in a time window, the one closest to the target visit will be used for analyses. If the two visits have the same distance from a target window, the later one will be used. If two or more visits have the same date and time (or a date but no time) then the average of these visits will be used. Both unscheduled and scheduled visit values will be considered (with no preference) for use in the analyses using the rules above.

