6.3. Appendix 3: Data Handling Conventions

Table 4: Analysis Visit Windowing

Assessment	Analysis Visit (Target Week [†])	Target Day*	Protocol Specified Visit window	Analysis Visit Windowing	
				Lower Limit	Upper Limit
Brief physical exam (height, weight, BMI)	Screening Visit 1	Day from initial dose	N/A	Day from initial dose	Day from initial dose
	Screening Visit 2	Day from initial dose	N/A	Day from initial dose	Day from initial dose
	Visit 5 (Week 4)	Day 28	± 3 days	Day 25	Day 31
	Visit 6 (Week 8)	Day 56	± 3 days	Day 53	Day 59
	Visit 9 (Week 14)	Day 98	± 3 days	Day 95	Day 101
	Visit 13 (Week 22)	Day 154	± 3 days	Day 151	Day 157
	Visit 14 (Day of Parturition)	Day of parturition [†]	± 3 days	Day of parturition – 3	Day of parturition + 3
	Visit 15 (4 weeks from Parturition)	Day 28 from Day of parturition	± 7 days	Day of Parturition + 20	Day of Parturition + 34
	Visit 16 (10 weeks from parturition)	Day 70 from Day of parturition	± 7 days	Day of Parturition + 62	Day of Parturition + 76

Parexel International

Rallybio IPA, LLC
IPA2202

Statistical Analysis Plan

Assessment	Analysis Visit (Target Week [†])	Target Day*	Protocol Specified Visit window	Analysis Visit Windowing	
				Lower Limit	Upper Limit
Vital signs	Screening Visit 2	Day from initial dose	N/A	Day from initial dose	Day from initial dose
	Visit 3 (Week 0)	Day 1	0	Day 1	Day 1
	Visit 6 (Week 8)	Day 56	± 3 days	Day 53	Day 59
	Visit 10 (Week 16)	Day 112	± 3 days	Day 109	Day 115
	Visit 14 (Day of Parturition)	Day of parturition [†]	± 3 days	Day of parturition – 3	Day of parturition + 3
	Visit 16 (10 weeks from parturition)	Day 70 from Day of parturition	± 7 days	Day of Parturition + 62	Day of Parturition + 76
12-lead ECG	Screening Visit 2	Day from initial dose	N/A	Day from initial dose	Day from initial dose
	Visit 14 (Day of Parturition)	Day of parturition [†]	± 3 days	Day of parturition – 3	Day of parturition + 3
	Visit 16 (10 weeks from parturition)	Day 70 from Day of parturition	± 7 days	Day of Parturition + 62	Day of Parturition + 76
Obstetric and fetal doppler ultrasound	Screening Visit 2	Day from initial dose	N/A	Day from initial dose	Day from initial dose
	Visit 5 (Week 4)	Day 28	± 3 days	Day 25	Day 31
	Visit 6 (Week 8)	Day 56	± 3 days	Day 53	Day 59
	Visit 8 (Week 12)	Day 84	± 3 days	Day 81	Day 87
	Visit 10 (Week 16)	Day 112	± 3 days	Day 109	Day 115
	Visit 12 (Week 20)	Day 140	± 3 days	Day 143	Day 137

Project Document Version No.:2.0; Document Effective Date: Date of last signature

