TP-GDO-WW-016-09

Effective Date: 22 Dec 21

Related to: SOP-GDO-WW-019

Page 49 of 70

Parexel International

Rallybio IPA, LLC
IPA2202

Statistical Analysis Plan

Assessment	Analysis Visit (Target Week [†])	Target Day*	Protocol Specified Visit window	Analysis Visit Windowing	
				Lower Limit	Upper Limit
	Visit 13 (Week 22)	Day 154	± 3 days	Day 151	Day 153
	Visit 14 (Day of Parturition)	Day of parturition [†]	± 3 days	Day of parturition – 3	Day of parturition + 3
Hematology, chemistry, coagulation, CRP	Screening Visit 2	Day from initial dose	N/A	Day from initial dose	Day from initial dose
	Visit 5 (Week 4)	Day 28	± 3 days	Day 25	Day 31
	Visit 8 (Week 12)	Day 84	± 3 days	Day 81	Day 87
	Visit 10 (Week 16)	Day 112	± 3 days	Day 109	Day 115
	Visit 14 (Day of Parturition)	Day of parturition [†]	± 3 days	Day of parturition – 3	Day of parturition + 3
	Visit 15 (4 weeks from Parturition)	Day 28 from Day of parturition [†]	± 7 days	Day of Parturition + 20	Day of Parturition + 34
	Visit 16 (10 weeks from parturition)	Day 70 from Day of parturition [†]	± 7 days	Day of Parturition + 62	Day of Parturition + 76
Urinalysis	Screening Visit 2	Day from initial dose	N/A	Day from initial dose	Day from initial dose
	Visit 5 (Week 4)	Day 28	± 3 days	Day 25	Day 31
	Visit 8 (Week 12)	Day 84	± 3 days	Day 81	Day 87
	Visit 10 (Week 16)	Day 112	± 3 days	Day 109	Day 115
	Visit 14 (Day of Parturition)	Day of parturition [†]	± 3 days	Day of parturition – 3	Day of parturition + 3

Project Document Version No.:2.0; Document Effective Date: Date of last signature

TP-GDO-WW-016-09

Effective Date: 22 Dec 21

Related to: SOP-GDO-WW-019

Page 50 of 70

Parexel International

Rallybio IPA, LLC
IPA2202

Statistical Analysis Plan

Assessment	Analysis Visit (Target Week [†])	Target Day*	Protocol Specified Visit window	Analysis Visit Windowing	
				Lower Limit	Upper Limit
	Visit 15 (4 weeks from Parturition)	Day 28 from Day of parturition	± 7 days	Day of Parturition + 20	Day of Parturition + 34
	Visit 16 (10 weeks from parturition)	Day 70 from Day of parturition	± 7 days	Day of Parturition + 62	Day of Parturition + 76
Study drug administration	Visit 3 (Week 0)	Day 1	0	Day 1	Day 1
	Visit 5 (Week 4)	Day 28	± 3 days	Day 25	Day 31
	Visit 6 (Week 8)	Day 56	± 3 days	Day 53	Day 59
	Visit 8 (Week 12)	Day 84	± 3 days	Day 81	Day 87
	Visit 10 (Week 16)	Day 112	± 3 days	Day 109	Day 115
	Visit 12 (Week 20)	Day 140	± 3 days	Day 143	Day 137

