	Visit 14 (Day of Parturition)	Day of parturition ^{†,‡}	± 24 hours [‡]	Day of parturition – 1	Day of parturition + 1
ADA	Visit 3 (Week 0)	Day 1	0	Day 1	Day 1
	Visit 5 (Week 4)	Day 28	± 3 days	Day 25	Day 31
	Visit 6 (Week 8)	Day 56	± 3 days	Day 53	Day 59
	Visit 8 (Week 12)	Day 84	± 3 days	Day 81	Day 87
	Visit 10 (Week 16)	Day 112	± 3 days	Day 109	Day 115
	Visit 12 (Week 20)	Day 140	± 3 days	Day 143	Day 137
	Visit 14 (Day of Parturition)	Day of parturition ^{†,‡}	± 24 hours [‡]	Day of parturition – 1	Day of parturition + 1

Project Document Version No.:2.0; Document Effective Date: Date of last signature

TP-GDO-WW-016-09

Effective Date: 22 Dec 21

Related to: SOP-GDO-WW-019

Page 51 of 70

Parexel International

Rallybio IPA, LLC
IPA2202

Statistical Analysis Plan

Assessment	Analysis Visit (Target Week [†])	Target Day*	Protocol Specified Visit window	Analysis Visit Windowing	
				Lower Limit	Upper Limit
	Visit 15 (4 weeks from Parturition)	Day 28 from Day of Parturition [†]	± 7 days	Day of Parturition + 20	Day of Parturition + 34
RLYB212 PK	Visit 3 (Week 0)	Day 1	0	Day 1	Day 1
	Visit 4 (Week 2)	Day 14	± 7 days	Day 8	Day 21
	Visit 5 (Week 4)	Day 28	± 3 days	Day 25	Day 31
	Visit 6 (Week 8)	Day 56	± 3 days	Day 53	Day 59
	Visit 7 (Week 10)	Day 70	± 7 days	Day 63	Day 77
	Visit 8 (Week 12)	Day 84	± 3 days	Day 81	Day 87
	Visit 9 (Week 14)	Day 98	± 7 days	Day 91	Day 105
	Visit 10 (Week 16)	Day 112	± 3 days	Day 109	Day 115
	Visit 11 (Week 18)	Day 126	± 7 days	Day 119	Day 133
	Visit 12 (Week 20)	Day 140	± 3 days	Day 143	Day 137
	Visit 13 (Week 22)	Day 154	± 7 days	Day 147	Day 164
	Visit 14 (Day of Parturition)	Day of parturition ^{†,‡}	± 24 hours [‡]	Day of parturition – 1	Day of parturition + 1
	Visit 15 (4 weeks from Parturition)	Day 28 from Day of parturition [†]	± 7 days	Day of Parturition + 20	Day of Parturition + 34
Pregnancy outcome	Visit 14 (Day of Parturition)	Day of parturition [†]	N/A	Day of Parturition	Day of Parturition
Cord blood sample	Visit 14 (Day of Parturition)	Day of parturition [†]	N/A	Day of Parturition	Day of Parturition
Newborn general status	Visit 14 (Day of Parturition)	Day of parturition [†]	N/A	Day of Parturition	Day of Parturition

Project Document Version No.:2.0; Document Effective Date: Date of last signature

TP-GDO-WW-016-09

Effective Date: 22 Dec 21

Related to: SOP-GDO-WW-019

Page 52 of 70

Parexel International

Rallybio IPA, LLC
IPA2202

Statistical Analysis Plan

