Assessment	Analysis Visit (Target Week [‡])	Target Day*	Protocol Specified Visit window	Analysis Visit Windowing	
				Lower Limit	Upper Limit
Infant general status	Visit 15 (4 weeks from Parturition)	Day 28 from Day of parturition [†]	± 7 days	Day of Parturition + 20	Day of Parturition + 34
	Infant EOS	12 months from Day of parturition [†]	± 14 days	Day of Parturition + 351.25	Day of Parturition + 379.25
HPA-1a alloantibodies	Screening Visit 1	Day from initial dose	N/A	Day from initial dose	Day from initial dose
	Visit 16 (10 weeks from parturition)	Day 70 from Day of parturition [†]	± 7 days	Day of Parturition + 62	Day of Parturition + 76

[‡] Number of weeks since initial dose.

* Number of days since initial dose (initial dose day is considered as Day 1) = (date of target visit – date of initial dose) + 1.

[†] Day of Parturition = (date of Parturition – date of initial dose) + 1.

[‡] Analysis visit window should be calculated from Date and time of parturition.

Project Document Version No.:2.0; Document Effective Date: Date of last signature

TP-GDO-WW-016-09

Effective Date: 22 Dec 21

Related to: SOP-GDO-WW-019

Page 53 of 70

Parexel International
Statistical Analysis Plan

Table 5: Clinical Laboratory Assessments

Laboratory Assessments	Parameters			
Hematology	Platelet count RBC count Hemoglobin Hematocrit	RBC indices: 
 • MCV • MCH • MCHC • % reticulocytes 		Platelet count WBC count with differential: 
 • Neutrophils • Lymphocytes • Monocytes • Eosinophils • Basophils
Clinical Chemistry	Urea Albumin Creatinine Glucose (nonfasting)	Potassium Sodium Calcium C-reactive protein	ALT/SGPT AST/SGOT GGT	Total bilirubin (and direct and indirect bilirubin) Total protein Alkaline phosphatase
Coagulation	Prothrombin time International normalized ratio Activated partial thromboplastin time			
Viral Serology	Hepatitis C virus antibody; Hepatitis B surface antigen (HBsAg); HIV antibody			
Routine Urinalysis	Specific gravity Dipstick for glucose, pH, nitrate, occult blood, ketones, bilirubin, urobilinogen, nitrite, and leukocyte esterase Microscopic examination (if blood or protein is abnormal)			
FNAIT Testing ^δ	FNAIT laboratory screening tests for maternal HPA-1a genotype, maternal HLA- DRB3*01:01 genotype, and maternal HPA-1 alloantibodyb, fetal HPA-1a genotype/cffDNA			

Parexel International

Rallybio IPA, LLC
IPA2202

Statistical Analysis Plan

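### SAP Table 4 breaks its own Day 1 rule: antenatal targets and most visit windows sit one day early, maternal postpartum limits are also a day early, and several Visit 12, Visit 13 and PK Visit 4 limits are wrong

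*SAP*

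**What the plan says.** SAP 4.1.3.3 commits to the protocol's windows: "The protocol specified visit windowing will be followed for all assessments". It points to the schedule (SAP Table 3) and to Table 4 in Appendix 3. The schedule allows ± 3 days for Visits 4 to 13 and ± 7 days for Visits 15 and 16. A cell note gives ± 7 days for the mid-interval PK samples.

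The day-numbering rule appears three times, always the same way:
- SAP 4.1.3.2: "For post-dose relative days = Assessment Date – first dosing date +1".
- Table 4 footnote: "Number of days since initial dose (initial dose day is considered as Day 1".
- Table 4 rows for the first dosing visit: "Visit 3 (Week 0) Day 1 0 Day 1 Day 1".

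The later antenatal rows read like "Visit 5 (Week 4) Day 28 ± 3 days Day 25 Day 31". Two Visit 13 rows stand out: "Visit 13 (Week 22) Day 154 ± 3 days Day 151 Day 153" for ultrasound and "Visit 13 (Week 22) Day 154 ± 7 days Day 147 Day 164" for PK. The lower limit for Visit 16, which covers the Week 10 alloantibody sample, is "Day of Parturition + 62".

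**The concern.** With first dose as Day 1 there is no Day 0, so Week 4 cannot be Day 28. The printed targets fit only a Day 0 origin, which the footnote and the Week 0 rows rule out. The table therefore contradicts itself, and its limits differ from the protocol windows that 4.1.3.3 says will be followed.

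At stake is which visit label a record carries, and which record is chosen when two fall in one window, because 4.1.3.3 takes the one nearest the target. For example, with records on Days 27 and 30, a target of 28 selects Day 27 (distances 1 and 2), while a target of 29 selects Day 30 (distances 2 and 1).

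**Working it through.** **Inputs.** Day = (visit date − first dose date) + 1, from SAP 4.1.3.2 and the Table 4 footnote. Windows come from the schedule. Table 4 has 38 antenatal post-dose rows across physical examination, vital signs, ultrasound, blood laboratory tests, urinalysis, dosing, ADA and PK.

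**The plan's own figure.** Day 28 for Week 4 is 7 × 4, which requires first dose = Day 0. Under the stated rule it is 7 × 4 + 1 = 29, with limits 29 ± 3 = 26 to 32.

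**± 3-day antenatal rows**

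| Week (visit) | Printed target (limits) | 7 × week + 1 (± 3) |
|---|---|---|
| 4 (Visit 5) | 28 (25–31) | 29 (26–32) |
| 8 (Visit 6) | 56 (53–59) | 57 (54–60) |
| 12 (Visit 8) | 84 (81–87) | 85 (82–88) |
| 14 (Visit 9, physical exam) | 98 (95–101) | 99 (96–102) |
| 16 (Visit 10) | 112 (109–115) | 113 (110–116) |
| 20 (Visit 12) | 140 (143–137) | 141 (138–144) |
| 22 (Visit 13, physical exam) | 154 (151–157) | 155 (152–158) |
| 22 (Visit 13, ultrasound) | 154 (151–153) | 155 (152–158) |

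Taking ± 7 days for the mid-interval PK rows, both limits are exactly one day early in 31 of 38 rows. Each such row loses one compliant day (1 of 7, or 1 of 15 for a ± 7-day window) and admits one day that is too early. In the Week 4 row, first dose + 31 days is Day 32 and falls outside, while first dose + 24 days is Day 25 and falls inside.

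**The other seven rows** (38 − 31 = 7)
- Visit 12 in ultrasound, dosing, ADA and PK (four rows): the lower limit, 143, exceeds the upper limit, 137. No day satisfies both, so all 7 compliant days are lost.
- Visit 13 ultrasound: the upper limit, 153, is below the table's own target, 154. Of compliant Days 152–158, five (154–158) are lost, and Day 151 is wrongly admitted. On the table's own arithmetic (154 ± 3 = 151–157), four of seven days are lost.
- Visit 13 PK: 154 + 7 = 161 and 155 + 7 = 162, but 164 is printed. Against 148–162 the printed row admits Days 147, 163 and 164 and loses none.
- PK Visit 4: printed 8–21. With target 15 and ± 7 the window is 8–22, so the lower limit is right and the upper limit is one day early.

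**Postpartum rows** (offsets from parturition, P; first-dose numbering plays no part)
- Visit 15: 28 ± 7 = P+21 to P+35; printed P+20 to P+34.
- Visit 16: 70 ± 7 = P+63 to P+77; printed P+62 to P+76.
- Infant end of study: 365.25 ± 14 = P+351.25 to P+379.25, as printed, so not shifted.

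The Visit 15 and 16 limits follow if delivery is counted as Day 1 (27 ± 7 and 69 ± 7). The infant end-of-study row uses a plain offset, so the table counts from parturition in two ways. The parturition rows (Visit 14) are not shifted.

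**Two conflicts that bear on the recalculation**
- The schedule's cell note gives ± 7 days for all mid-interval PK samples, but the text beneath the schedule confines ± 7 days to Weeks 30 and 38 (Visits 9 and 13). Under ± 3 days, Visits 4, 7 and 11 would be 12–18, 68–74 and 124–130. All lie inside the printed 8–21, 63–77 and 119–133, so no compliant sample at those visits is lost on that reading. The count of 31 then becomes 29, because Visits 7 and 11 leave it.
- The protocol places the infant visit at 4–6 weeks, that is P+28 to P+42. The infant Visit 15 row ends at P+34. Moving it to P+35 would still leave P+36 to P+42 outside.

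**The case against.** The strongest reply is that nothing now depends on these windows. SAP 4.9 replaces every table and figure with listings for the single enrolled participant. Even under the full plan, ultrasound results were to be listed only (SAP 4.2.2.6) and the individual PK plots use actual elapsed time (SAP 4.2.1.1). This stands and limits the importance of the point. It does not remove it: 4.9 does not withdraw Table 4, and version 2.0 of the SAP records typo corrections yet leaves these rows as they are.

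A reader might infer that women seen on the last allowed day drop out of the analysis, or that a Week 10 alloantibody result at P+77 is lost. The documents do not support that. The Alloimmunization Analysis Set asks only for a postpartum determination and sets no window, so a P+77 sample stays in the set. What it misses is the printed Visit 16 window. That a record outside every window goes without a visit label is itself an inference: the SAP gives no rule for such records and no fallback to the nominal visit.

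Nor is every row affected alike. The Visit 13 PK row drops no compliant day, the Visit 13 physical examination row has only the one-day shift, and the infant end-of-study row is not shifted.

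**Conclusion.** The error is confirmed as an internal contradiction in Table 4. All 38 antenatal targets are one day early under the SAP's own rule. Both limits are one day early in 31 rows, or 29 if the narrower PK window applies. Maternal Visits 15 and 16 are one day early for a separate reason, the counting of parturition. The largest single defects are the empty Visit 12 window in four rows and the Visit 13 ultrasound window that excludes its own target.

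The conclusion assumes that the Day 1 rule, stated three times, is the intended one, and that the schedule's ± 3 and ± 7 days are measured from exact weeks after first dose or parturition. The effect on the final report is small: it concerns analysis-visit labels in listings for one participant. It would have mattered more for the by-visit summaries planned before early termination.

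**What to change.** In Table 4:
1. Replace the ± 3-day antenatal rows with the right-hand column of the table in the working. This also repairs the reversed Visit 12 limits and the Visit 13 ultrasound limit.
2. Set the maternal Visit 15 and Visit 16 limits to the recomputed offsets, and state that parturition is counted as day 0 for these rows.
3. For the mid-interval PK rows, first reconcile the schedule's cell note with the text beneath it, then apply the agreed window around 7 × week + 1. If ± 7 days is kept throughout, the limits are Visit 4: 8–22; Visit 7: 64–78; Visit 9: 92–106; Visit 11: 120–134; Visit 13: 148–162.
4. Reconcile the infant Visit 15 row with the protocol's 4–6 week visit before setting its limits.
5. Add a sentence on how records outside every window are labelled.

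These changes concern analysis labels only and alter no dosing or visit schedule. Given the reduced scope, a sufficient alternative is one sentence in SAP 4.9 saying that Table 4 windows are not applied and that listings show nominal visits. Either way the cost is a text or table edit, with no new data.
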